6.4.2 Follow-up of unresolved adverse events

Any AEs that are unresolved at the time of the 30 day follow-up, must be followed up by the investigator through to resolution, and whilst the database is open should be recorded on the database.

AstraZeneca retains the right to request additional information for any patient with ongoing AE(s)/SAE(s) at the end of the study, if judged necessary.

6.4.3 Adverse events after the 30 day follow-up period

For Pharmacovigilance purposes and characterisation of events of special interest, any case of MDS/AML or new primary malignancy, as well as pneumonitis occurring after the 30 day follow up period should be reported as SAE (or AE for non-melanoma skin cancers, if at least one of the criteria for SAE is not met, see Section 6.2) to AstraZeneca Patient Safety regardless of investigator's assessment of causality. A Questionnaire will be sent to any investigator reporting MDS/AML or new primary malignancy or pneumonitis as an aid to provide detailed information on the case.

At any time after a patient has completed the study, if an investigator learns of any SAE including death, and he/she considers there is a reasonable possibility that the event is causally related to the investigational product, the investigator should notify AstraZeneca, Patient Safety.

If patients who are gaining clinical benefit are allowed to continue study treatment post data cut-off and/or post study completion then all SAEs must continue to be collected and reported to Astra Zeneca Patient Safety within the usual timeframe.

Otherwise after study treatment completion (i.e., after any scheduled post treatment follow-up period has ended), there is no obligation to actively report information on new AEs or SAEs occurring in former study patients. This includes new AEs/SAEs in patients still being followed up for survival but who have completed the post treatment follow-up period (30 days).

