6. SAFETY REPORTING AND MEDICAL MANAGEMENT

The Principal Investigator is responsible for ensuring that all staff involved in the study are familiar with the content of this section.

6.1 **Definition of adverse events**

An adverse event is the development of an undesirable medical condition or the deterioration of a pre-existing medical condition following or during exposure to a pharmaceutical product,

whether or not considered causally related to the product. An undesirable medical condition can be symptoms (e.g., nausea, chest pain), signs (e.g., tachycardia, enlarged liver) or the abnormal results of an investigation (e.g., laboratory findings, electrocardiogram). In clinical studies, an AE can include an undesirable medical condition occurring at any time, including run-in or washout periods, even if no study treatment has been administered.

The term AE is used to include both serious and non-serious AEs.

6.2 **Definitions of serious adverse event**

A serious adverse event is an AE occurring during any study phase (i.e., run-in, treatment, washout, follow-up), that fulfils one or more of the following criteria:

- Results in death
- Is immediately life-threatening
- Requires in-patient hospitalisation or prolongation of existing hospitalisation
- Results in persistent or significant disability/incapacity or substantial disruption of the ability to conduct normal life functions
- Is a congenital abnormality or birth defect
- Is an important medical event that may jeopardise the patient or may require medical intervention to prevent one of the outcomes listed above.

For further guidance on the definition of a SAE, see Appendix B 'Additional Safety Information' to the Clinical Study Protocol.

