6.3 Adverse events of special interest

Adverse events of special interest (AESI) for olaparib are events of scientific and medical interest specific to the further understanding of olaparib's safety profile and require close monitoring and rapid communication by the investigators to AstraZeneca. An AESI may be serious or non-serious. Adverse Events of Special Interest for olaparib are the important potential risks of MDS/AML, new primary malignancies (other than MDS/AML) and pneumonitis type events.

Any event of MDS/AML, new primary malignancy (other than MDS/AML), or pneumonitis should be reported to AstraZeneca Patient Safety whether it is considered a non-serious AE (e.g. non-melanoma skin cancer) or SAE, and regardless of investigator's assessment of causality. These adverse events must be reported according to the timelines for reporting an SAE (see Section 6.4) to allow timely safety monitoring. A questionnaire will be sent to any investigator reporting an AESI, as an aid to provide further detailed information on the event. During the study there may be other events identified as AESIs that require the use of a

questionnaire to help characterise the event and gain a better understanding regarding the relationship between the event and study treatment.

6.4 **Recording of adverse events**

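### Section 6.4.3 inverts the seriousness test for late non-melanoma skin cancer, and its rule for late pneumonitis needs reconciling with Section 6.3

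*Protocol*

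**What the plan says.** Four places in the protocol bear on how a late event of special interest is classed.

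- **Section 6.2** defines an SAE as an AE in any study phase, follow-up included, "that fulfils one or more of the following criteria". Six criteria follow. One reads "Is a congenital abnormality or birth defect"; another is the important medical event.
- **Section 6.3** names MDS/AML, other new primary malignancies and pneumonitis as events of special interest. It states "An AESI may be serious or non-serious" and asks for a report to the sponsor's safety department "whether it is considered a non-serious AE (e.g. non-melanoma skin cancer) or SAE, and regardless of investigator's assessment of causality". It adds: "These adverse events must be reported according to the timelines for reporting an SAE".
- **Section 6.4.3** covers the period after the 30-day follow-up, which runs from the last dose. Any late case of MDS/AML, new primary malignancy or pneumonitis "should be reported as SAE (or AE for non-melanoma skin cancers, if at least one of the criteria for SAE is not met", with a pointer to Section 6.2. The bracketed clause is the only exception.
- **Section 6.4.9** treats a new primary cancer, skin cancer included, as an AE that can usually be expected to satisfy one or more of the Section 6.2 criteria.

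Sections 3.9.1 and 4.3.5 also ask for these late events to be reported, but do not say how to class them.

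**The concern.** The exception in Section 6.4.3 is meant to separate serious from non-serious late skin cancers by the Section 6.2 criteria. As worded it cannot, because its condition is true of every such case.

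This touches what is recorded. Section 6.4.4 asks for the applicable seriousness criteria, the hospitalisation and discharge dates and the date the event became serious only for SAEs. A serious late skin cancer filed as an AE on the literal wording would not carry those fields. AEs, SAEs and events of special interest are the outcome measure of the safety objective (Section 2.3), and late new primary malignancies belong to a named exploratory objective (Section 2.4), so the rule should be right.

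The same sentence raises a second, separate question. It files every late pneumonitis as an SAE, with no provision for a case that meets no seriousness criterion, although Section 6.3 allows such a case to be non-serious.

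**Working it through.** There is no figure in the plan to reproduce. The check is a comparison of two rules.

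**Inputs.** Six criteria from Section 6.2, each met or not met. The Section 6.2 rule and the Section 6.4.3 exception are taken as written.

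**The two rules for a late non-melanoma skin cancer.**

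- Section 6.2: SAE if at least one criterion is met. Its complement is that none is met.
- Section 6.4.3, literally: AE if at least one criterion is unmet. Its complement, and so the only way to be an SAE, is that all six are met.

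**All six criteria free.** There are 2^6 = 64 patterns.

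- Section 6.2 gives SAE in 64 − 1 = 63 (all but the pattern with none met).
- Section 6.4.3 gives SAE in 1 (all six met).
- The rules agree only when none or all are met, so they disagree in 64 − 2 = 62.

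**Birth-defect criterion fixed at not met**, as it must be for an acquired adult cancer. There are 2^5 = 32 patterns.

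- Section 6.2 gives SAE in 32 − 1 = 31.
- Section 6.4.3 gives SAE in 0.
- The rules disagree in 31.

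These are counts of logical patterns, not of patients. They show that the exception, read literally, leaves no route to SAE. Death or hospitalisation alone makes the event serious under Section 6.2 and an AE under Section 6.4.3.

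**After correction.** If the exception applies only when none of the criteria is met, the two rules agree in 64 of 64 patterns, and in 32 of 32 with the birth-defect criterion fixed.

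**Pneumonitis.** This does not turn on the negation. Section 6.4.3 gives SAE in every pattern, including the one with no criterion met. Section 6.3 allows that pattern to be a non-serious AE and already secures fast reporting by applying SAE timelines, without changing the class. The two passages cover the same event after the 30-day period, since Section 6.3 sets no time limit, and they do not say the same thing about its class.

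**The case against.** The strongest reply is that no sensible investigator would follow the literal wording. The clause points to Section 6.2, which applies to follow-up and would itself make a fatal or hospitalised case serious. Section 6.4.9 states the test the right way round and mentions skin cancer. Section 6.4.4 records for every AE whether it is serious. This stands as an argument about practical effect. It does not make the wording right: the sentence still states the wrong condition, in the one place that governs late cases.

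On pneumonitis, the reply is that Section 6.4.3 sets a cautious default for pharmacovigilance, that the important-medical-event criterion lets the sponsor treat pneumonitis as serious, and that reporting as an SAE may describe only a route. The first two points stand: there is no clear conflict with Section 6.2, and the default is partly the sponsor's choice. The third is possible but unstated, and the same sentence contrasts SAE with AE by the Section 6.2 criteria, which sounds like classification. The mismatch with Section 6.3 therefore remains.

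A reader might also infer that serious events of special interest before and after the 30-day boundary could not be added or compared. The protocol does not support that. It plans no such comparison, and it collects seriousness, CTCAE grade and outcome, which would help in reviewing how a case was classed. Section 6.3 has these events reported on SAE timelines whatever their class, so no report need be lost.

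**Conclusion.** The skin-cancer exception in Section 6.4.3 is wrong as written. It inverts the Section 6.2 test and, read literally, files every late non-melanoma skin cancer as an AE. This rests on the literal scope of the negation and on the fact that an acquired cancer is not a birth defect. The intended meaning can be inferred, so the practical effect is probably small and the point is minor.

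The pneumonitis rule is a real inconsistency with Section 6.3, to be reconciled, but not an established conflict with Section 6.2.

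It would go too far to conclude that in this trial no late skin cancer could ever be recorded as serious, since Sections 6.2, 6.4.4 and 6.4.9 all point the other way. Nor can a number of affected patients be given. The protocol states no rate for these events, and only misclassified cases would count: skin cancers that meet a criterion but are filed as AEs, and pneumonitis that meets none but is filed as an SAE. That number could be zero. No efficacy estimate or analysis set depends on the point.

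**What to change.** 1. In Section 6.4.3, change the bracketed exception so that a late non-melanoma skin cancer is reported as an AE *if none of the criteria for SAE is met, see Section 6.2*. This alters one phrase and leaves reporting timelines and workload unchanged.
2. Reconcile Section 6.4.3 with Section 6.3 on late pneumonitis. State whether reporting as an SAE sets the class of the event or only the reporting route. If it sets the class, say that this is a deliberate default and note it in Section 6.3. If it sets only the route, say that seriousness follows Section 6.2 while SAE timelines apply to every case. The second choice would move any late pneumonitis that meets no criterion from SAE to non-serious in the tables.
3. Leave the SAE default for late MDS/AML and the other new primary malignancies as it is, unless the sponsor chooses to change it. A single rewording that classes all late events of special interest by Section 6.2 would remove that default too, and should not be adopted without saying so.

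The cost is a change to one or two sentences, which can go into the next amendment.

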6.4.4 Variables

The following variables will be collect for each AE:

- AE (verbatim)
- The date and time when the AE started and stopped
- Max CTCAE grade and changes in CTCAE grade
- Whether the AE is serious or not
- Investigator causality rating against the IP (yes or no)
- Action taken with regard to IP
- AE caused patient's withdrawal from study (yes or no)>>
- Outcome.

In addition, the following variables will be collected for SAEs:

- Date AE met criteria for serious AE
- Date Investigator became aware of serious AE
- AE is serious due to (provide all seriousness criteria applicable)
- Date of hospitalisation (if applicable)
- Date of discharge (if applicable)
- Probable cause of death (if applicable)
- Date of death (if applicable)
- Autopsy performed (yes or no; if yes provide report) (if applicable)
- Causality assessment in relation to study procedure(s)
- Description of serious AE.

For each episode on an adverse event, all changes to the CTCAE grade attained as well as the highest attained CTCAE grade should be reported.

It is important to distinguish between serious and severe AEs. Severity is a measure of intensity whereas seriousness is defined by the criteria in Section 6.1. An AE of severe intensity need not necessarily be considered serious. For example, nausea that persists for several hours may be considered severe nausea, but not a SAE unless it meets the criteria shown in Section 6.2. On the other hand, a stroke that results in only a limited degree of disability may be considered a mild stroke but would be a SAE when it satisfies the criteria shown in Section 6.2.

The grading scales found in the National Cancer Institute (NCI) CTCAE version 4.0 will be utilised for all events with an assigned CTCAE grading. For those events without assigned CTCAE grades the recommendation is that the CTCAE criteria that convert mild, moderate and severe events into CTCAE grades should be used.

A copy of the CTCAE version can be downloaded from the Cancer Therapy Evaluation program website (http://ctep.cancer.gov).

6.4.5 **Causality collection**

The investigator will assess causal relationship between Investigational Product and each Adverse Event, and answer 'yes' or 'no' to the question 'Do you consider that there is a reasonable possibility that the event may have been caused by the investigational product?'

For SAEs causal relationship will also be assessed for other medication and study procedures. Note that for SAEs that could be associated with any study procedure the causal relationship is implied as 'yes'.

A guide to the interpretation of the causality question is found in Appendix B 'Additional Safety Information' to the Clinical Study Protocol.

6.4.6 Adverse events based on signs and symptoms

All AEs spontaneously reported by the patient or care provider or reported in response to the open question from the study personnel: '*Have you had any health problems since the previous visit/you were last asked?*', or revealed by observation will be collected and recorded in the CRF. When collecting AEs, the recording of diagnoses is preferred (when possible) to recording a list of signs and symptoms. However, if a diagnosis is known and there are other signs or symptoms that are not generally part of the diagnosis, the diagnosis and each sign or symptom will be recorded separately.

6.4.7 **Hy's Law**

Cases where a patient shows elevations in liver biochemistry may require further evaluation and occurrences of AST or $ALT \ge 3xULN$ together with total bilirubin $\ge 2xULN$ may need to be reported as SAEs. Please refer to Appendix D for further instruction on cases of increases in liver biochemistry and evaluation of Hy's Law.

6.4.8 **Disease progression**

Disease progression can be considered as a worsening of a patient's condition attributable to the disease for which the investigational product is being studied. It may be an increase in the severity of the disease under study (DUS) and/or increases in the signs and symptoms of the cancer. The development of new, or progression of existing metastasis to the primary cancer under study should be considered as disease progression and not an AE. Events, which are unequivocally due to disease progression, should not be reported as an AE during the study.

6.4.9 New cancers

The development of a new primary cancer (including skin cancer) should be regarded as an AE and will generally meet at least one of the serious criteria (see Section 6.2). New primary cancers are those that are not the primary reason for the administration of the study treatment and have developed after the inclusion of the patient into the study. They do not include metastases of the original cancer. Symptoms of metastasis or the metastasis itself should not be reported as an AE/SAE, as they are considered to be disease progression.

6.4.10 Lack of efficacy

When there is deterioration in the ovarian cancer, for which the study treatment(s) is being used, there may be uncertainty as to whether this is lack of efficacy or an AE. In such cases, unless the Sponsor or the reporting physician considers that the study treatment contributed to the deterioration of the condition, or local regulations state to the contrary, the deterioration should be considered to be a lack of efficacy and not an AE.

6.4.11 **Deaths**

All deaths that occur in screening Part 1 related to study procedures should be reported as a SAE.

All deaths that occur during the study, or within the protocol defined 30 day post study follow up period after the administration of the last dose of study treatment, must be reported as follows:

- Death clearly the result of disease progression should be reported to the study monitor at the next monitoring visit and should be documented in the eCRF but should not be reported as an SAE.
- Where death is not due (or not clearly due) to progression of the disease under study, the AE causing the death must be reported to the study monitor as a SAE within 24 hours (see Section 6.2 for further details). The report should contain a comment regarding the co-involvement of progression of disease, if appropriate, and should assign main and contributory causes of death. This information can be captured in the 'Death eCRF'.
- Deaths with an unknown cause should always be reported as a SAE. A post mortem maybe helpful in the assessment of the cause of death, and if performed a copy of the post-mortem results should be forwarded to AstraZeneca within the usual timeframes.

6.5 **Reporting of serious adverse events**

In screening Part 1, only SAEs related to study procedures must be reported. From screening Part 2 onwards, all SAEs have to be reported, whether or not considered causally related to the investigational product, or to the study procedure(s). All SAEs will be recorded in the CRF.
If any SAE occurs in the course of the study, then investigators or other site personnel inform the appropriate AstraZeneca representatives immediately, but **no later than 24 hours** of when he or she becomes aware of it.

The designated AstraZeneca representative works with the investigator to ensure that all the necessary information is provided to the AstraZeneca Patient Safety data entry site within 1 calendar day of initial receipt for fatal and life threatening events and within 5 calendar days of initial receipt for all other SAEs.

For fatal or life-threatening adverse events where important or relevant information is missing, active follow-up is undertaken immediately. Investigators or other site personnel inform designated AstraZeneca representatives of any follow-up information on a previously reported SAE within one calendar day i.e., immediately but **no later than 24 hours** of when he or she becomes aware of it.

Once the investigators or other site personnel indicate an AE is serious in the WBDC system, an email alert is sent to the designated AstraZeneca representative.

If the WBDC system is not available, then the investigator or other study site personnel reports a SAE to the appropriate designated AstraZeneca representative by telephone.

The designated AstraZeneca representative will advise the investigator/study site personnel how to proceed.

The reference document for definition of expectedness/listedness is the IB or the Prescribing Information (Appendix G) as applicable based on country specific marketing authorisation status for the AstraZeneca drug.

6.6 **Overdose**

There is currently no specific treatment in the event of overdose with olaparib and possible symptoms of overdose are not established.

Olaparib must only be used in accordance with the dosing recommendations in this protocol. Any dose or frequency of dosing that exceeds the dosing regimen specified in this protocol should be reported as an overdose.

Adverse reactions associated with overdose should be treated symptomatically and should be managed appropriately:

- An overdose with associated AEs is recorded as the AE diagnosis/symptoms on the relevant AE modules in the CRF and on the Overdose CRF module.
- An overdose without associated symptoms is only reported on the Overdose CRF module.

If an overdose on an AstraZeneca study drug occurs in the course of the study, then the investigator or other site personnel inform appropriate AstraZeneca representatives immediately, or **no later than 24 hours** of when he or she becomes aware of it.

The designated AstraZeneca representative works with the investigator to ensure that all relevant information is provided to the AstraZeneca Patient Safety data entry site.

For overdoses associated with a SAE, the standard reporting timelines apply, see Section 6.5. For other overdoses, reporting must occur within 30 days.

6.7 **Pregnancy**

All pregnancies and outcomes of pregnancy should be reported to AstraZeneca.

6.7.1 Maternal exposure

If a patient becomes pregnant during the course of the study olaparib should be discontinued immediately.

Pregnancy itself is not regarded as an adverse event unless there is a suspicion that the investigational product under study may have interfered with the effectiveness of a contraceptive medication. Congenital abnormalities/birth defects and spontaneous miscarriages should be reported and handled as SAEs. Elective abortions without complications should not be handled as AEs. The outcome of all pregnancies (spontaneous miscarriage, elective termination, ectopic pregnancy, normal birth or congenital abnormality) should be followed up and documented even if the patient was discontinued from the study.

If any pregnancy occurs during the course of the study, then the Investigator or other site personnel informs the appropriate AstraZeneca representatives within 1 day i.e., immediately but **no later than 24 hours** of when he or she becomes aware of it.

The designated AstraZeneca representative works with the Investigator to ensure that all relevant information is provided to the AstraZeneca Patient Safety data entry site within 1 or 5 calendar days for SAEs (see Section 6.5) and within 30 days for all other pregnancies.

The same timelines apply when outcome information is available.

The PREGREP module in the CRF is used to report the pregnancy and the PREGOUT is used to report the outcome of the pregnancy.

6.7.2 **Paternal exposure**

Not applicable.

6.8 **Management of IP related toxicities, dose interruptions and dose reductions**

Study treatment may be temporarily interrupted to manage adverse reactions such as nausea, vomiting, diarrhoea, and anaemia and dose reduction can be considered. The recommended dose reduction is to 200 mg twice daily (equivalent to a total daily dose of 400 mg). If a further final dose reduction is required, then reduction to 100 mg twice daily (equivalent to a total daily dose of 200 mg) could be considered. In cases where any transfusions to manage anaemia and or thrombocytopenia are needed, these should be recorded with date, type and units given.

6.9 **Study governance and oversight**

Not applicable.

6.9.1 **Steering Committee**

Not applicable.

6.9.2 **Data Monitoring Committee**

Not applicable.

